8.2.2.2 Randomized Treatment Period

Induction Phase

During the 4-week Induction phase patients will remain on their optimized dose of OCS along with their baseline asthma medications.

Oral Corticosteroid Reduction Phase

The OCS dose will be down-titrated during this phase following a predetermined schedule, provided in Table 2, dependent upon the patient's optimized OCS dose (the OCS dose the patient was receiving at the time of randomization). Dose reductions will occur every 4 weeks which should allow for carryover effects from the previous dose to be minimized and also minimize the risk for clinically significant events. The last possible dose reduction can occur at Week 20 with no further dose adjustments beyond this time point.

Time course				OCS dose (mg/day)					
Optimized OCS dose	35	30	25	20	15	12.5	10	7.5	5
First dose reduction	25	20	15	10	10	10	5	5	2.5
+4 week	15	10	10	5	5	5	2.5	2.5	0
+4 week	10	5	5	2.5	2.5	2.5	0	0	
+4 week	5	2.5	2.5	0	0	0			
+4 week	2.5	0	0						

Table 2 Oral corticosteroid titration schedule during the Oral Corticosteroid Reduction phase

OCS=oral corticosteroid

A clinical assessment should be completed prior to each dose reduction. The reduction in OCS dose should occur per the schedule provided in Table 2.

OCS Reduction Phase Interruption Criteria

Primary reasons for not following the scheduled dose reduction include:

- Change in ACQ-5 score ≥ 0.5 from the prior month OCS dose assessment
- Clinically significant asthma exacerbation(s)
- FEV₁ 20% reduction from baseline stability limit
- Mean morning peak expiratory flow (PEF) <70% of baseline stability limit as assessed in the week prior to the clinical visit
- Rescue medication use requiring 4 or more puffs/day above the mean baseline value for any 2 consecutive days in the prior week, or ≥12 puffs on any 1 day in the week prior to the clinical visit
- Clinically significant event, based on investigator judgment that requires treatment by OCS dose adjustment

The Investigator should decide, depending on the reason for not reducing the OCS dose per schedule, whether to maintain or increase his/her current OCS dose by 1 step.

Maintenance Phase

Patients will be maintained for the last 4 weeks of the Randomized Treatment period on the same OCS dose established at Week 20; however, the Investigator should decide whether to maintain or increase the current OCS dose by 1 step based on the OCS reduction phase interruption criteria.

Oral Corticosteroid Dose after an Asthma Exacerbation

If a severe asthma exacerbation occurs during the Reduction or Maintenance phase of the Randomized Treatment period, the exacerbation should be treated (see Section 8.2.5 for treatment of severe asthma exacerbations). Following resolution, the patient should be placed on the OCS dose 1 step higher than that which he/she was on when the exacerbation occurred for at least

4 weeks and continue with dose reductions as per Table 2 at the following visit. If a second exacerbation occurs, the OCS dose should be increased 1 step; however, no further OCS dose reductions will be allowed.

8.2.3 Posttreatment/Follow-up Period

During this follow-up period, patients will continue treatment with their stable dose of OCS. The dose of OCS can be modified based on their level of asthma control, as determined by the Investigator.

8.2.4 Reliever Medication

Patients may administer albuterol/salbutamol or levalbuterol/levosalbutamol metered dose inhaler (MDI) as reliever medication as needed during the study. Nebulizer solutions may be used as an alternative delivery method.

8.2.5 Treatment of severe asthma exacerbations

Severe asthma exacerbations will be treated with the use of oral or parenteral corticosteroids at a dose at least equivalent to double the dose of current maintenance dose of OCS for a minimum of 3 days to a maximum of 7 days, this is to ensure that exacerbations are managed in a timely manner and consistently, when possible, for all patients participating in this study. If the exacerbation is not resolved after 7 days, the treatment of the exacerbation may continue at the discretion of the Investigator.

8.2.6 Treatment after the end of the study

The Investigator is responsible for ensuring that consideration has been given to the post study care of the patient's medical condition.

Patients who complete the 24-week treatment period, and return for the EOT visit at Week 24, may be eligible to roll over into a long-term study.

At the end of the study, patients who do not roll over into a long-term study may be prescribed appropriate alternative asthma therapy if needed and as determined by the study Investigator.

8.3 BLINDING PROCEDURES

8.3.1 Methods of blinding

Dupilumab and placebo will be provided in identically matched 2 mL prefilled syringes. To protect the blind, each treatment kit of 2 mL (dupilumab or placebo) glass prefilled syringe will be prepared such that the treatments (dupilumab or placebo) are identical and indistinguishable and will be labeled with a treatment kit number. The randomized treatment kit number list will be generated by Sanofi.

Both the patient and the Investigator will be blinded to the assigned active drug or placebo. Study patients, Investigators, and study site personnel will not have access to the randomization (treatment codes) except under circumstances described in Section 8.3.2.

Patients, Investigators, and site personnel will not have access to assay results for immunoglobulins (IgG, IgG subclasses, IgA, and IgM) after the first administration of IMP because these values have the potential for unblinding. Furthermore, neither patients, investigators, nor site personnel will have access to eotaxin-3, antigen-specific IgE, thymus and activation-regulated chemokine (TARC), or periostin while the study is ongoing or upon study completion, as the related data are not essential for patient care and have the potential for unblinding.

The DMC will receive blinded results by treatment group or unblinded (if necessary) confidential reports from an independent statistician for review, which have to be handled None of these reports can be delivered to unauthorized persons.

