 Hospital Anxiety and Depression Scale (HADS) EQ-5D-5L
 Change from baseline at Weeks 2, 4, 8 12, 16, 20, and 24 in:
 Morning/evening asthma symptom score and nocturnal awakenings (eDiary)
- Use of rescue medication
- Health Care Resource Utilization
Exploratory endpoints
Blood samples for exploratory genetic analysis of DNA and RNA to assess the relationship of DNA variants and/or gene expression with asthma and response to dupilumab treatment
Biomarkers
- Fractional exhaled nitric oxide (FeNO) levels
- Blood eosinophil count
 Total and antigen-specific immunoglobulin (Ig)E

[figure not shown]
	- Thymus and activation-regulated chemokine (TARC)		
	- Periostin		
	- Eotaxin-3		
	 Sputum and blood, interleukin (IL) C2 and CD34 cells, and cytokines (at selected study sites in Canada) 		
	Change from baseline in airway hyperresponsiveness at Week 24 (at selected study sites within Canada)		
ASSESSMENT SCHEDULE	 Screening period (from 3 to up to 8 weeks [up to 10 weeks for patients who experience an asthma exacerbation that requires a change in OCS dose to allow for 2 weeks of stabilization prior to randomization]) 		
	 Randomized Treatment period (up to 24 weeks) 		
	Post-treatment period (12 weeks)		
STATISTICAL CONSIDERATIONS	Sample size determination		
	The sample size estimation is based on the comparison between dupilumab versus placebo in regards to the primary endpoint and the key secondary endpoint: percentage reduction of OCS dose at Week 24 compared with the baseline dose and proportion of patients achieving a reduction of 50% or greater in their OCS dose compared with baseline at Week 24, while maintaining asthma control. For the primary endpoint, assuming a common standard deviation of 50%, with 90 randomized patients per group, the study will have 94% power to detect a treatment difference of 27% at the 2-tailed significance level of α =0.05. For the key secondary endpoint, with the same sample size of 90 randomized patients per group, the study will have 81% power to detect a difference in the proportion of patients achieving 50% or greater in their OCS dose of 33% in the placebo group, compared to 54% in the dupilumab group at the 2-tailed significance level of α =0.05. Patients will be randomized using a 1:1 randomization ratio for dupilumab		
	300mg q2w and placebo. Randomization will be stratified by optimized OCS dose at Week 0 (\leq 10 mg/day, >10 mg/day) and country.		

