8.3.2 Randomization code breaking during the study

In case of an adverse event (AE), the code should only be broken in circumstances when knowledge of the IMP is required for treating the patient.

Code breaking can be performed at any time by using the proper module of the interactive voice response system (IVRS)/interactive web response system (IWRS) and/or by calling any other phone number provided by the Sponsor for that purpose. If the blind is broken, the Investigator should document the date, time of day, and reason for code breaking.

Patient withdrawal will only occur when the code break call is made at the site level, not the study level. This means that if the emergency unblinding transaction is performed by the Investigator (ie, at the site level), then the patient will be withdrawn from treatment. However, if the emergency unblinding transaction is performed by the Global Safety Officer (GSO; ie, at the study level, as the GSO is not site based), then the patient will not be withdrawn from treatment. At the facilities where the systemic drug concentration measurements, ADA, and selected biomarkers are determined, the samples will be analyzed prior to data base lock leading to unblinding of responsible bioanalysts. Bioanalysts are excluded from the clinical trial team.

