9.2.2.4.1 Asthma Control Questionnaire-5 question version

The ACQ-5 is a 5-item questionnaire, which has been developed as a measure of patients' asthma control that can be quickly and easily completed in clinical practice (14). The questions are designed to be self-completed by the patient. The 5 questions enquire about the frequency and/or severity of symptoms (nocturnal awakening on waking in the morning, activity limitation, shortness of breath, and wheezing). The response options for all these questions consist of a 0 (no impairment/limitation) to 6 (total impairment/limitation) scale (Appendix D). The ACQ-5 score is a mean of the values recorded for the individual questions.

Throughout the study patients should complete the ACQ-5 on a weekly basis using their eDiary. The results from the ACQ-5 will be used as a part of the assessment to determine patient eligibility for OCS dose adjustment. The patient should complete the questionnaire within the eDiary. The patient should be instructed to complete the questions as accurately as possible. The patient should be reassured that there are no right or wrong answers. If the patient requests help or clarification with any of the questions, he/she will be asked to reread the instructions and give the answer that best reflects how he/she felt over the previous week. The Investigator should not provide the patient with any answer or attempt to interpret any portion of a question.

If the ACQ-5 is completed through the eDiary while the patient is at a scheduled in-clinic visit, it is recommended that the ACQ-5 be administered at the same time during the visit. To avoid biasing responses, the patients should not be told the results of diagnostic tests prior to completing the questionnaire and should be completed before any procedures are performed on the patient to avoid influencing the patient's response. Adequate time should be allowed to complete all items on the ACQ-5.

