- Serum immunoglobulins: quantitative immunoassays for total IgG, IgG subclasses 1-4, IgM, and IgA (after the first administration of IMP, results are blinded to the sites and sponsor study team).

Amended Clinical Trial Protocol 02 EFC13691 - dupilumab 25-Jan-2017 Version number: 1

• Clinical laboratory testing at Visit 1 and Visit 10 adds hepatitis screen including HBsAg, HBsAb, IgM and IgG/total-HBcAb, HCVAb, HIV screening (anti-HIV-1 and anti-HIV-2 antibodies), and anti-nuclear antibody (ANA). Note: anti-double-stranded DNA antibody will be tested if ANA is positive (≥1:160 titer). Patients who are IgG/total-HBcAb positive and HBsAg negative at Visit 1 must undergo HBV DNA testing prior to randomization to determine eligibility (only applicable for patients who plan to roll over into a long term study). In case of results showing HCVAb positive, HCV RNA testing must be negative prior to randomization.

Decision trees for the management of certain laboratory abnormalities by Sanofi are provided in Appendix F.

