9.2.6 Pharmacodynamics

Pharmacodynamics is an exploratory endpoint.

Several biomarkers related to asthmatic inflammation and Th2 polarization will be assessed for their value in predicting therapeutic response and/or in documenting the time course of drug response. In 2 prior asthma trials (ACT11457 and DRI12544), treatment with dupilumab significantly suppressed systemic levels of serum TARC (CCL17; a ligand of CCR4 receptors that attracts Th2 cells), plasma eotaxin-3 (CCL26; a ligand of CCR3 receptors that attracts eosinophils and lung mast cells), and serum total IgE (a product of immunoglobulin class switching driven by IL-4), as well as reduced the concentrations of FeNO (a marker of airway inflammation). Periostin (a protein reported to be elevated at baseline in patients responsive to treatment with anti-IL-13 antibodies) is included to differentiate dupilumab from the anti-IL-13 therapeutic class.

Assay methodologies are briefly summarized below. More detailed information on the collection, handling, transport and preservation of samples (eg, minimum volumes required for blood collection and for aliquots for each biomarker assay) will be provided in a separate laboratory manual.

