2.1.7 Pharmacodynamics/genomics endpoints

PD endpoints include:

- Whole blood biomarkers: Blood eosinophil count will be measured as part of the standard clinical lab test at Visits 1 (Week -8 to -3), 3 (Week 0), 5 (Week 4), 7 (Week 8), 8 (Week 12), 9 (Week 16), 10 (Week 20), 11 (Week 24), 14 (Week 36)
- Plasma biomarkers: Eotaxin-3 measured at Visits 3 (Week 0), 5 (Week 4), 8 (Week 12), 10 (Week 20), 11 (Week 24)
- Serum biomarkers: Antigen-specific IgE, Total IgE, TARC, and periostin at Visits 3 (Week 0), 5 (Week 4), 8 (Week 12), 10 (Week 20), 11 (Week 24)
- Fractional exhaled nitric oxide: will be measured at every visit
- **ILC2 and CD34 cells and cytokines in sputum and blood** (optional; only for patients enrolled in select sites in Canada): Innate lymphoid type 2 (ILC2) cells and CD34+ cells will be measured in the blood and induced sputum. Cytokines will be assayed in the sputum and blood. At Visits 3 (Week 0) and 11 (Week 24), both sputum and blood will be collected. At Visit 14, only a sputum sample will be collected (for patients who have not entered into the long-term study).
Pharmacogenetic testing is optional and voluntary. For those patients who sign the optional pharmacogenetic informed consent form, blood samples for exploratory genetic analysis of DNA or RNA will be collected at Visit 3 (Week 0). The DNA or RNA samples may be used to determine a possible relationship between genes and response to treatment with dupilumab, possible adverse reactions to dupilumab, and to study the genetics of asthma. The DNA may be subjected to a genome-wide association study by whole genome array (common single nucleotide polymorphisms) analysis and/or to whole exome sequencing or whole genome analysis in order to thoroughly explore genetic associations with disease progression or treatment response. The RNA may be subjected to discrete panels of polymerase chain reaction (PCR) analyses, microarray analyses, or RNA sequencing analyses.

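### The blinding section withholds TARC and eotaxin-3 from sites but not total IgE or FeNO, though dupilumab is said to lower all four: an avoidable unblinding risk of unknown size

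*Protocol*

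**What the plan says.** Protocol 8.3.1 has two lists of results kept from patients, investigators and site personnel. The first covers IgG, its subclasses, IgA and IgM once dosing has begun. The second reads "neither patients, investigators, nor site personnel will have access to eotaxin-3, antigen-specific IgE, thymus and activation-regulated chemokine (TARC), or periostin", and applies both during the study and after it ends, "as the related data are not essential for patient care and have the potential for unblinding".

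Protocol 9.2.6 describes what dupilumab did in two earlier asthma trials. It suppressed TARC and eotaxin-3, "and serum total IgE (a product of immunoglobulin class switching driven by IL-4), as well as reduced the concentrations of FeNO".

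Total IgE is elsewhere grouped with the withheld assays. The synopsis has one biomarker line, "Total and antigen-specific immunoglobulin (Ig)E". SAP 2.1.7 lists the serum markers together, "Antigen-specific IgE, Total IgE, TARC, and periostin at Visits 3 (Week 0", and then at Weeks 4, 12, 20 and 24. The same SAP section has FeNO measured at every visit.

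Three other provisions touch on masking:
- Protocol 9.2.3.5, on IgG, IgG subclasses, IgM and IgA: "after the first administration of IMP, results are blinded to the sites and sponsor study team".
- Protocol 8.3.2, on the laboratories: "Bioanalysts are excluded from the clinical trial team".
- Protocol 9.2.2.4.1, on the ACQ-5: "To avoid biasing responses, the patients should not be told the results of diagnostic tests prior to completing the questionnaire". An ACQ-5 done in clinic is also to come before that visit's procedures.

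**The concern.** The reason given for withholding TARC and eotaxin-3 seems to apply to total IgE and, at least on the unblinding half, to FeNO. An investigator who sees FeNO fall over successive visits has a hint about the arm.

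That matters because the primary endpoint is a dose the investigator sets. Under Protocol 8.2.2.2 a scheduled OCS reduction can be withheld for an event that the investigator judges to need an OCS change, and the investigator then chooses between holding the dose and raising it one step. Protocol 9.1.1 uses the same kind of judgment to define asthma control between Weeks 20 and 24. Someone who believes a patient is on dupilumab might hold or step up less readily, and someone who believes the patient is on placebo more readily. Either tendency would favor dupilumab.

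The SAP would not reveal this. The analyses in SAP 2.4.4.1.2 and 2.4.4.1.3 deal with missing data, non-normality and data after treatment discontinuation.

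**Working it through.** The plan gives no figure to reproduce here. The check is a comparison of lists and schedules.

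**Step 1: drug-responsive markers against the withheld lists.** The in-clinic visits after randomization at which a reduction can be decided are Visits 5, 7, 8, 9 and 10, at Weeks 4, 8, 12, 16 and 20 (Protocol 1.1 and 10.1.2). Sampling times are from SAP 2.1.7.

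| Marker lowered (Protocol 9.2.6) | Withheld in 8.3.1 | Measured or sampled at titration visits |
|---|---|---|
| TARC | yes | 3 of 5 (Weeks 4, 12, 20) |
| Eotaxin-3 | yes | 3 of 5 (Weeks 4, 12, 20) |
| Total IgE | not named | 3 of 5 (Weeks 4, 12, 20) |
| FeNO | not named | 5 of 5 |

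Withheld: 2 of 4. Section 8.3.1 also withholds periostin and antigen-specific IgE, for which 9.2.6 reports no dupilumab effect.

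**Step 2: does another provision close the gap?** Section 9.2.3.5 stops at IgG, its subclasses, IgM and IgA. Section 8.3.2 separates laboratory analysts from the trial team but does not say what is reported to sites. Section 9.2.2.4.1 restricts what the patient hears before a questionnaire, not what the investigator sees. Sections 9.2.6.3 and 9.2.6.4 describe how total IgE and FeNO are measured and do not mention masking. None closes it.

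**Step 3: how much FeNO could be seen, and when.** Readings after the first dose up to the last permitted reduction are at Weeks 2, 4, 6, 8, 12, 16 and 20, which is 7. Two of them (Weeks 2 and 4), plus the Week 0 value, are scheduled by the first possible reduction. FeNO precedes spirometry (9.2.6.4), so where the FEV1 criterion is checked at the visit, the FeNO reading exists before the dose decision. The four phone contacts (Weeks 10, 14, 18, 22) have no scheduled FeNO, although flow chart footnotes o and q let OCS changes occur outside clinic visits.

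**Step 4: how wide the judgment route is.** Section 8.2.2.2 lists six reasons for not reducing. Four have numerical thresholds: ACQ-5, FEV1, morning PEF and rescue use. FeNO is not among the six. Influence would run through the remaining discretion: the investigator-judged event and the hold-or-increase choice. The control judgment in 9.1.1 rests on the same kind of event, and the analyzed value is computed from the baseline and final doses (11.4.2.1). These are best counted as one route acting through the final dose.

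**Step 5: size.** The documents give no effect size for FeNO or total IgE, no measure of how well either separates individual patients by arm, and no statement of who sees the values. No bias can be computed.

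**The case against.** A reader might infer that sites receive total IgE results, or that the blind was in fact broken. The documents support neither. Total IgE is a serum assay whose handling is left to a laboratory manual that was not supplied, and absence from a withheld list is not evidence of disclosure. FeNO also has its own manual, not supplied, which may already mask the reading.

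A reader might also call 8.3.1 self-contradictory over FeNO. It is not. It gives two reasons together, no need for patient care and potential to unblind, and nothing says that FeNO meets the first. That objection stands, and it is why the FeNO change has to be conditional.

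The investigator will have other clues anyway. FEV1 (improved in Phase 2b, Protocol 4.2.2), PEF and rescue use are titration criteria and must stay visible. Injection site reactions are the stated exception to adverse event balance (4.2.2), and sites must monitor them closely (10.6.2). What FeNO adds is therefore unknown. The ACQ-5 input is also better protected than it first appears, because an in-clinic ACQ-5 precedes that visit's procedures, although readings from earlier visits could still be known.

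Finally, masking FeNO is not free. Protocol 10.2 treats downloaded nitric oxide data as source data, and 13.1 gives the investigator duties over data and source documents.

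These points limit the weight of the concern. They do not explain why 8.3.1 leaves out two markers that the protocol itself reports as lowered by the drug.

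**Conclusion.** The point holds as an avoidable functional-unblinding risk of unknown size. It is not a shown breach of the blind and not a demonstrated bias in the primary endpoint.

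The two markers carry different weight. FeNO matters more: it is a procedure performed at the visit and is scheduled at every in-clinic titration visit. For total IgE the point is mainly that the withheld list omits an assay that belongs with its neighbors.

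The conclusion assumes that the unseen manuals do not already mask these values and that, where FeNO is visible, the investigator deciding the OCS dose could see it. If the manuals do mask either marker, what remains is to align 8.3.1 with them. The change is worth making because the quantity protected is the primary endpoint and the cost is low.

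**What to change.** 1. **Total IgE.** Add it in 8.3.1 to the results withheld from patients, investigators and site personnel after the first dose of study drug. Beyond biomarker summaries (SAP 2.4.6.2), the SAP uses only the baseline value, in its definition of an atopic condition (SAP 2.1.1), and that stays available. There is no material downside.

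2. **FeNO.** State in 8.3.1 and in the FeNO manual that values after randomization are not disclosed to the patient or to the investigator deciding the OCS dose, unless the sponsor judges FeNO necessary for patient care. Existing site staff would handle the reading, and the source-data provisions in 10.2 and 13.1 would be aligned.

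The FeNO change brings a small site burden where one person now both measures FeNO and decides the dose; the documents do not say who measures it. Protection would be incomplete, because whoever runs the test may see the value. No dose, titration rule, visit or sample size changes.
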